2.3.1 Rationale for ibrutinib dose and schedule

Ibrutinib will be administered at the standard approved dose in CLL, 420 mg orally administered daily. See ibrutinib package insert for additional information.

2.3.2 Rationale for VAY736 dose and schedule

Based on PK/PD modeling developed for RA patients and simulation adjusted for B cell baseline and dynamics in CLL patients, the proposed starting dose of VAY736 is 0.3 mg/kg i.v. Q2W.

[REDACTED]. Additionally, 90% B cell depletion is associated with the mitigation of neutropenia risk and the recovery of absolute neutrophil counts, as described in [Section 1.2.2.3](#). A dose-escalation approach will be undertaken in order to determine the appropriate dose in combination with ibrutinib. The dose of VAY736 will be escalated in sequential cohorts guided by a BLRM and following clinical review of available data as described in [Section 2.2](#).

2.4 Rationale for choice of combination drugs

See [Section 2.1](#).

2.5 Rationale for choice of comparators drugs

Not applicable

2.6 Risks and benefits

Appropriate eligibility criteria and specific DLT definitions, as well as specific dose modification and stopping rules, are included in this protocol. The risk to subjects in this trial may be minimized by compliance with the eligibility criteria and study procedures, as well as close clinical monitoring. There may be unforeseen risks with the combination of VAY736 with ibrutinib which could be serious. Refer to the latest version of the [VAY736 Investigators Brochure] and the ibrutinib package insert for more information.

[REDACTED]

[REDACTED]

2.7 Rationale for Public Health Emergency mitigation procedures

During a Public Health emergency as declared by Local or Regional authorities i.e. pandemic, epidemic or natural disaster, mitigation procedures to ensure participant safety and trial integrity are listed in relevant sections. Notification of the Public health emergency should be discussed with Novartis prior to implementation of mitigation procedures, and permitted/approved by Local or Regional Health Authorities and Ethics Committees as appropriate.

[figure not shown]
[REDACTED]

3 Objectives and endpoints

Objectives and related endpoints are described in [Table 3-1](#) below.

Table 3-1 Objectives and related endpoints

Objective	Endpoint	Analysis
Primary		Refer to Section 10.4
To determine the MTD and/or RD of the combination of VAY736 with ibrutinib	Safety Escalation only: 
Incidence of DLTs in cycle 1 (28 days) Escalation and expansion: 
Incidence and severity of AEs and SAEs, including changes in laboratory parameters and vital signs Tolerability Dose interruptions, reduction, and dose intensity	
To characterize the safety and tolerability of the combination of VAY736 and ibrutinib		Refer to Section 10.5
Secondary		
To assess any preliminary antitumor activity of the combination	Rate of patients with CR as assessed by investigators per IWCLL at cycle 9 day 1 Overall response rate (ORR) assessed by investigators per IWCLL criteria and Time To Progression (TTP) Clearance of ibrutinib resistance mutations (BTKC481 and/or PLC γ 2 hotspot), defined as less than 1% mutation bearing alleles (Arm B only).	
To characterize the PK of VAY736 and ibrutinib when used in combination therapy	Plasma concentration of VAY736 and ibrutinib, and derived parameters	
To assess immunogenicity (IG) following one or more intravenous infusions of VAY736	Presence of anti-VAY736 antibodies	

Objective	Endpoint	Analysis

[figure not shown]
4 Study design

4.1 Description of study design

The MTD and/or RDE of the combination of VAY736 with ibrutinib will be determined in this open-label phase Ib dose escalation trial. Upon identification of the MTD or RDE, an expansion part will be opened to patient enrollment to further characterize the safety, PK, and pharmacodynamics (PD) of the combination.

Both the dose escalation and dose expansion parts will enroll patients with CLL who are currently receiving ibrutinib therapy following relapse on another approved therapy AND have either failed to achieve a CR after > 1 year of ibrutinib treatment OR who have developed a resistance mutation to ibrutinib without clinical relapse at any time during treatment. The dose expansion part of the study will also include patients who have received ibrutinib either alone or in combination (or have received ibrutinib continuously with multiple sequential combination partners) as first-line therapy and have either failed to achieve a complete response after 1 year of therapy or have developed a resistance mutation to ibrutinib. Approximately 15-20 patients will be enrolled to the dose escalation part of the study. In the expansion part, approximately 40 patients will be enrolled to two arms (approximately 20 patients in each arm). One arm will enroll patients who have been on ibrutinib treatment for more than one year with evidence of residual disease and which places them at risk for clinical relapse; the other arm will enroll patients with acquired resistance mutations to ibrutinib who have not yet demonstrated clinical relapse, see [Figure 4-1](#). All patients with acquired resistance mutations who are enrolled to the dose expansion part of the study will be enrolled in Arm B, irrespective of ibrutinib treatment duration.

Patients will receive the combination of VAY736 and ibrutinib for 6 cycles. Starting with C7D1, VAY736 will be discontinued if the patient has achieved a CR per IWCLL response criteria with no evidence of disease per radiological assessment and normal blood counts at C6D15. Ibrutinib will be administered per protocol for an additional two cycles (through C8D28). If a patient has not achieved a CR per IWCLL response criteria at C6D15, VAY736 and ibrutinib will be continued for 2 additional cycles (Cycle 7 and Cycle 8). At C9D1 (± 7 days), patients will have their final disease assessment [REDACTED] of the study. All patients who have remained on study, including those who have discontinued treatment due to reasons other than disease progression, will be assessed at this time point. For patients who achieve a complete response at this assessment, investigators may consider discontinuing ibrutinib in order to follow patients for durability of response and minimize intolerance and toxicity associated with continuous ibrutinib therapy while maximizing patient quality of life.

Figure 4-1 Study design

* Combination administered for either 6 cycles or 8 cycles, ibrutinib continued through C8D28. For patients who achieve a CR at the primary endpoint (C9D1), investigators may consider discontinuing ibrutinib.

**Patients will be evaluated for the final disease assessment on C9D1 (\pm 7 days) in accordance with IWCLL guidelines.

4.2 Timing of interim analyses and design

The dose-escalation design foresees that decisions on future dose levels based on available data are taken at the end of each cohort. These are described in [Section 6.2.3](#) and [Section 10.7](#).

The RD will be selected based on a review by Novartis study personnel and Investigators of available safety and tolerability information (including the DLT risk assessment from the BLRM using EWOC) along with PK, PD and efficacy data. The expansion part will then begin as specified in [Section 4.1](#).

Details about the timing and interim analysis decisions can be found in [Section 10.7](#).

4.3 Definition of end of study

The study will end when all patients have completed the treatment period, safety period and two-year efficacy follow-up or have been lost to follow-up, discontinued the study for any reason, or the study is terminated early.

See [Section 10](#) for details of timing of the primary analysis and final reporting of data.

4.4 Early study termination

The study can be terminated at any time for any reason by Novartis. Should this be necessary, the patient should be seen as soon as possible and the same assessments should be performed as described in [Section 7](#) for a discontinued or withdrawn patient. The investigator may be informed by the sponsor of additional procedures to be followed in order to ensure that adequate consideration is given to the protection of the patient's interests. The investigator will be responsible for informing IRBs and/or ECs of the early termination of the trial.

5 Population

5.1 Patient population

The study will enroll patients with CLL who are currently taking ibrutinib therapy following relapse from another approved therapy AND have either failed to achieve a CR after >1 year of ibrutinib treatment OR who have developed a resistance mutation to ibrutinib without clinical relapse at any time during treatment. The dose expansion part of the study will also include patients who have received ibrutinib either alone or in combination (or have received ibrutinib continuously with multiple sequential combination partners) as first-line therapy and have failed to achieve a complete response after 1 year of therapy or have developed a resistance mutation to ibrutinib. Patients must be taking and tolerating ibrutinib at time of enrollment with no limits to their continued ibrutinib use.

The investigator or designee must ensure that only patients who meet all the following inclusion and none of the exclusion criteria are offered treatment in the study.

5.2 Inclusion criteria

Patients eligible for inclusion in this study have to meet **all** of the following criteria:

Patient must meet the following laboratory values at the screening visit unless cytopenias are related to CLL:

1. Diagnosis of chronic lymphocytic leukemia (CLL) meeting criteria established in the World Health Organization (WHO) classification of hematologic disorders or International Workshop on Chronic Lymphocytic Leukemia (IWCLL) ([Hallek et al 2018](#)). Variant immunophenotype and prolymphocytic morphology change after diagnosis of CLL is allowed.
2. Age \geq 18 years
3. [REDACTED]
4. Male patients agree to avoid fathering a child as per the ibrutinib package insert

5. Dose escalation:
 - a. On ibrutinib > 1 year following relapse from another approved therapy without achieving a complete response

[figure not shown]
OR
 - b. On ibrutinib following relapse with another approved therapy and the presence of a known ibrutinib resistance mutation (BTK or PLC γ 2) at ≥ 1 variant allele frequency OR $< 1\%$ with two separate measurements at least 4 weeks apart with increasing variant allele frequency.
6. Dose expansion:
 - a. Arm A: On ibrutinib > 1 year following relapse from another approved therapy without achieving a complete response and patients who have received ibrutinib either alone or in combination (or have received ibrutinib continuously with multiple sequential combination partners) as first-line therapy and have failed to achieve a complete response after 1 year.
 - b. Arm B: On ibrutinib following relapse with another approved therapy and patients who have received ibrutinib either alone or in combination (or have received ibrutinib continuously with multiple sequential combination partners) as first-line therapy and the presence of a known ibrutinib resistance mutation at $\geq 1\%$ variant allele frequency OR $< 1\%$ with two separate measurements at least 4 weeks apart with increasing variant allele frequency. *Note: As of Amendment 6, patients will no longer be enrolled into Arm B.
7. Ibrutinib dose:
 - Escalation: Patients must be receiving 420 mg ibrutinib
 - Expansion: Patients may be on a dose of ibrutinib lower than 420 mg. Any dose must have been stable for 2 months prior to the start of study treatment.
8. Absolute Neutrophil Count ≥ 750 cells/ μ L ($0.75 \times 10^9/L$) independent of growth factor support within 7 days of the first dose of VAY736
9. Platelets $\geq 25 \times 10^9/L$ without transfusion support within 7 days of the first dose of study drug. Patients with transfusion dependent thrombocytopenia are excluded.
10. Hemoglobin (Hgb) ≥ 8 g/dL without transfusion support within 7 days prior to the first dose of VAY736.
11. Creatinine Clearance ≥ 30 mL/min using Cockcroft-Gault formula (or similar institutional standard) or creatinine $< 2 \times$ ULN
12. Total bilirubin $\leq 1.5 \times$ ULN (For patients with Gilbert's Syndrome: total bilirubin $< 3.0 \times$ ULN with direct bilirubin $< 1.5 \times$ ULN)
13. Aspartate transaminase (AST) $\leq 3.0 \times$ ULN
14. Alanine transaminase (ALT) $\leq 3.0 \times$ ULN
15. Eastern Cooperative Oncology Group (ECOG) performance status 0-2.
16. Written informed consent must be obtained prior to any screening procedures.
17. Patients with relapsed disease after prior allogeneic stem cell transplant (myeloablative or nonmyeloablative) will be eligible if they meet all other inclusion criteria and:
 - a. Do not have active (chronic or acute) GVHD and no immunosuppression
 - b. Are more than 6 months from transplant

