6.3.1.1 VAY736

Dose interruptions and/or reductions for VAY736 are recommended in order to allow patients to continue the study treatment. Upon the first dose adjustment, the dose of VAY736 should be reduced to the next lowest safe dose (or the -1 dose if toxicity occurs in the first cohort) as described in [Table 6-2](#). Dose reduction below -1 dose level is not permitted. These dose modifications are summarized in [Table 6-4](#). Each patient is allowed only 2 dose reductions of VAY736. Further dose reduction may be permitted for patients who have benefitted from treatment upon documented agreement by Novartis. A patient must discontinue treatment if, after treatment is resumed at a lower dose, the toxicity recurs with the same or worse severity.

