6.3.1.3 VAY736 and ibrutinib

Any dose changes must be recorded on the Dosage Administration Record eCRF.

If a patient requires a dose interruption of > 28 days of either VAY736 or ibrutinib from the intended day of the next scheduled dose, then the patient must be discontinued from the study unless otherwise specified in [Section 6.1.5](#). Patients who discontinue the study for a study related adverse event or an abnormal laboratory value must be followed as described in [Section 6.3.2](#).

Table 6-4 Criteria for dose reduction / interruption and re-initiation of VAY736 treatment for adverse drug reactions.

Dose modifications for VAY736	
Worst toxicity CTCAE Grade ^a (value) during a cycle of therapy	
Investigations (Hematologic)	
Neutropenia (ANC)	
Grades 1 -3	Maintain dose level
Grade 4 (ANC < 500/mm3)	Hold VAY736 until ANC $\geq 0.5 \times 10^9/L$, then resume VAY736 at same dose levels (with G-CSF support) or lower dose levels at investigator discretion.
Thrombocytopenia	
Grade 4 (PLT < 25,000/mm3)	Hold VAY736 until \leq Grade 3 then resume VAY736 at same dose levels or lower dose levels at investigator discretion
Febrile neutropenia (ANC < $1.0 \times 10^9/L$, fever $\geq 38.5^{\circ}C$)	Hold VAY736 until ANC $\geq 0.75 \times 10^9/L$, then resume VAY736 at same dose levels (with G-CSF support) or lower dose levels at investigator discretion.
Investigations (Renal)	
Serum creatinine	
Grade 1 (> ULN - 1.5 x ULN)	May maintain dose level
Grade 2 (> 1.5 - 3.0 x ULN)	Delay study treatment until resolved to Grade 1 or baseline If resolved by ≤ 7 days maintain dose level If resolved ≥ 7 days reduce one dose level
Grade 3 (> 3.0 - 6.0 x ULN)	Delay study treatment until resolved to Grade 1 or baseline If resolved by ≤ 7 days maintain dose level If resolved ≥ 7 days reduce dose of VAY736
Grade 4 (> 6.0 x ULN)	Omit dose and discontinue patient from study drug treatments
Investigations (Hepatic)	
Isolated total Bilirubin elevation	
> ULN – 1.5 x ULN	Maintain dose level
> 1.5 - 3.0 x ULN	Omit dose. Monitor LFTs ^b weekly, or more frequently if clinically indicated, until resolved to $\leq 1.5 \times$ ULN. If resolved in ≤ 7 days, then maintain dose level If resolved in > 7 days, then $\downarrow 1$ dose level

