> 3.0 - 10.0 x ULN*	
Omit dose. Monitor LFTs^b weekly, or more frequently if clinically indicated, until resolved to \leq 1.5 x ULN:
 
If resolved in \leq 7 days, then \downarrow 1 dose level
 
If resolved in $>$ 7 days, then discontinue patient from study drug treatments. The patient should be monitored weekly (including LFTs^b), or more frequently if clinically indicated, until total bilirubin have resolved to baseline or stabilization over 4 weeks.

> 10.0 x ULN*	
Discontinue patient from study drug treatments
 
The patient should be monitored weekly (including LFTs^b), or more frequently if clinically indicated, until total bilirubin have resolved to baseline or stabilization over 4 weeks.

Isolated AST or ALT elevation	
> ULN - 3.0 x ULN	Maintain dose levels
> 3.0 - 5.0 x ULN	
For patients with baseline value \leq 3.0 x ULN	Maintain dose levels. Repeat LFTs ^b as soon as possible, preferably within 48-72 hours from awareness of the abnormal results; if abnormal lab values are confirmed upon the repeat test, then monitor LFTs ^b weekly, or more frequently if clinically indicated, until resolved to \leq 3.0 x ULN
For patients with baseline value $>$ 3.0 -5.0 x ULN	Maintain dose levels
> 5.0 - 10.0 x ULN	
For patients with baseline value \leq 3.0 x ULN	Omit doses. Repeat LFTs ^b as soon as possible, preferably within 48-72 hours from awareness of the abnormal results; monitor LFTs ^b weekly, or more frequently if clinically indicated, until resolved to \leq 3.0 x ULN Then
	If resolved in \leq 7 days, maintain dose level
	If resolved in $>$ 7 days, \downarrow 1 dose level
For patients with baseline value $>$ 3.0 -5.0 x ULN	Maintain dose level. Repeat LFTs ^b as soon as possible, preferably within 48-72 hours from awareness of the abnormal results; if abnormal lab values are confirmed upon the repeat test, then monitor LFTs ^b , weekly, or more frequently if clinically indicated, until resolved to \leq 5.0 x ULN
> 10.0 - 20.0 x ULN	Omit dose. Repeat LFTs ^b as soon as possible, preferably within 48-72 hours from awareness of the abnormal results; monitor LFTs ^b weekly, or more frequently if clinically indicated, until resolved to \leq baseline. Then \downarrow 1 dose level.
> 20.0 x ULN	Discontinue patient from study drug treatment

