Grade 2	Maintain dose level, but initiate/intensify appropriate skin toxicity therapy (such as antihistamines, topical corticosteroids and low-dose systemic corticosteroids)
Grade 3, despite skin toxicity therapy	Omit dose until resolved to Grade \leq 1, then: If resolved in \leq 7 days, then \downarrow 1 dose level If resolved in $>$ 7 days (despite appropriate skin toxicity therapy), then discontinue patient from study drug treatment
Grade 4, despite skin toxicity therapy	Omit dose Discontinue patient from study drug treatment
Infusion Reaction	
Grade 1	Decrease infusion rate until recovery
Grade 2	Stop infusion Before restarting – pre-medicate as outlined in Section 6.1.2 . Restart infusion at 50% of previous rate under continuous observation. Ensure that there is a minimum observation period of 1 hour prior to restarting the infusion(s) If the AE recurs at the reinitiated slow rate of infusion, and despite pre-medication, then discontinue patient from study
Grade 3 or 4	Discontinue treatment
Other adverse events	
Grade 1 or 2	Maintain dose level
Grade 3 or 4	Hold VAY736 until resolved to \leq Grade 1 or baseline. If toxicity resolves within 7 days, resume at the same dose. If treatment delay is $>$ 7 days and \leq 28 days, restart at lower dose level of the VAY736. If delay is greater than 28 days, discontinue treatment.

All dose modifications should be based on the worst preceding toxicity.

^a Common Toxicity Criteria for Adverse Events (CTCAE Version 4.03)

^b Core LFTs consist of ALT, AST, GGT, total bilirubin (fractionated [direct and indirect], if total bilirubin > 2.0 x ULN), and alkaline phosphatase (fractionated [quantification of isoforms], if alkaline phosphatase > 2.0 x ULN.)

^c "Combined" defined as total bilirubin increase to the defined threshold concurrently with ALT/AST increase to the defined threshold

If combined elevations of AST or ALT and total bilirubin do not meet the defined thresholds, please follow the instructions for isolated elevation of total bilirubin and isolated elevation of AST/ALT, and take a conservative action based on the degree of the elevations (e.g. discontinue treatment at the situation when omit dose is needed for one parameter and discontinue treatment is required for another parameter). After all elevations resolve to the defined thresholds that allow treatment re-initiation, re-start the treatment either at the same dose or at one dose lower if meeting a criterion for dose reduction

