^d "Cholestasis" defined as ALP elevation (>2.0 xULN and R value <2) in patients without bone metastasis, or elevation of ALP liver fraction in patients with bone metastasis

Note: The R value is calculated by dividing the ALT by the ALP, using multiples of the ULN for both values. It denotes whether the relative pattern of ALT and/or ALP elevation is due to cholestatic (R ≤ 2), hepatocellular (R ≥ 5), or mixed (R >2 and < 5) liver injury

* Note: If total bilirubin > 3.0 x ULN is due to the indirect (non-conjugated) component only, and hemolysis as the etiology has been ruled out as per institutional guidelines (e.g., review of peripheral blood smear and haptoglobin determination), then ↓ 1 dose level and continue treatment at the discretion of the investigator.

** Note: antidiarrheal medication is recommended at the first sign of abdominal cramping, loose stools or overt diarrhea

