6.3.2 Follow-up for toxicities

Patients whose treatment is interrupted or permanently discontinued due to an adverse event or clinically significant laboratory value, must be followed up at least once a week (or more frequently if required by institutional practices, or if clinically indicated) for 4 weeks, and subsequently at approximately 4-week intervals, until resolution or stabilization of the event, whichever comes first. Appropriate clinical experts such as ophthalmologist, endocrinologist, dermatologist, psychiatrists etc. should be consulted as deemed necessary.

Table 6-5 outlines the follow-up evaluation recommended for toxicities of specific types and CTCAE grades.

Table 6-5 Follow-up evaluations for selected toxicities

TOXICITY	FOLLOW-UP EVALUATION
Blood and lymphatic system disorders	If CTCAE Grade 4 neutropenia, thrombocytopenia or anemia, or febrile neutropenia occurs, test pertinent labs at least weekly until resolution to baseline or stabilization.
Hepatic	If a hepatic adverse event occurs, ALT, AST and total bilirubin must be measured at least once a week until resolution to CTCAE Grade \leq 1 or baseline. In patients with total bilirubin Grade \geq 2 (any duration) bilirubin should be fractionated into total/direct or indirect/direct components and any additional evaluation as clinically indicated by these results should be performed
Investigations (metabolic)	Test twice weekly until \leq CTCAE grade 2, continue to test weekly until resolution to \leq CTCAE grade 1 or stabilization. Amylase or lipase \geq CTCAE grade 3 A CT scan or equivalent imaging procedure to assess the pancreas, liver, and gallbladder is recommended within 7 days of the first occurrence of any \geq CTCAE grade 3 result, to exclude disease progression or potential other liver disease. In patients with serum triglycerides \geq 500 mg/dL, urine amylase also needs to be tested.
Cardiac disorders QT and ECG ECG changes indicative of ischemic event	Twice weekly ECGs until normalization or stabilization of ECG findings

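### Criterion 12 admits Gilbert's patients with total bilirubin above 1.5 and below 3.0 x ULN, but Table 6-4 gives that band no baseline or Gilbert's branch, so a rise within it may block restart

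*Protocol*

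**What the plan says.** Protocol Section 5.2, criterion 12, caps total bilirubin at 1.5 x ULN and then makes an exception. "For patients with Gilbert's Syndrome: total bilirubin" may be anything below 3.0 x ULN, provided direct bilirubin is below 1.5 x ULN.

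Table 6-4 (Section 6.3.1.3) deals with isolated total bilirubin above 1.5 and up to 3.0 x ULN by omitting the dose. Liver tests are then monitored "weekly, or more frequently if clinically indicated, until resolved to" 1.5 x ULN or less. The dose level is kept if that takes 7 days or less, and drops by one level if it takes longer. The row mentions neither baseline nor Gilbert's Syndrome. The table's only provision for indirect bilirubin is a footnote to the two higher rows: "Note: If total bilirubin > 3.0 x ULN is due to the indirect (non-conjugated) component only". In that case, once hemolysis is excluded, VAY736 goes down one level and treatment continues at the investigator's discretion.

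Other rows of the same table do use baseline:
- Creatinine: "Delay study treatment until resolved to Grade 1 or baseline".
- AST/ALT: separate instructions headed "For patients with baseline value", for baselines up to 3.0 and for above 3.0 to 5.0 x ULN.
- Other adverse events of Grade 3 or 4: held to "Grade 1 or baseline. If toxicity resolves within 7 days, resume at the same dose".

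Table 6-5 also accepts baseline as the end of hepatic follow-up: "ALT, AST and total bilirubin must be measured at least once a week until resolution to CTCAE Grade" 1 or less, or baseline.

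**The concern.** The band that criterion 12 opens for Gilbert's patients is almost exactly the band in which Table 6-4 stops dosing. These patients enter with a raised value that the protocol has accepted, and the restart threshold lies below it. Once a rise within the band puts the row into effect, falling back to the entry value does not release the hold.

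At stake is whether an eligible patient who tolerates treatment loses VAY736, and with it ibrutinib, over a bilirubin level accepted at entry. Sites may also treat the same patient differently. Some will apply the row to the absolute value, and others will rely on the table's title and the adverse event definition.

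**Working it through.** No sample size or error rate is involved. The check sets the thresholds side by side and follows one patient through the rules.

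**Entry range against dosing rule**

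| Finding | Can it be present at entry? | Does Table 6-4 allow for baseline? |
|---|---|---|
| Total bilirubin >1.5 to <3.0 x ULN, direct <1.5 x ULN | Yes, in Gilbert's (criterion 12) | No |
| Total bilirubin >3.0 x ULN, indirect only | No | No, but the footnote permits one level down |
| AST/ALT baseline >3.0 to 5.0 x ULN | No (criteria 13 and 14: up to 3.0) | Yes, with maintain-dose branches |
| Creatinine >1.5 x ULN (Grade 2) | Yes, below 2 x ULN (criterion 11) | Yes |

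The AST/ALT rows provide for a baseline that nobody can have, while the bilirubin row has nothing for a baseline that criterion 12 admits. SAP Section 5.3 grades total bilirubin above 1.5 to 3.0 x ULN as Grade 2, so these patients enter at Grade 2.

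**Worked patient (assumed values)**

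Entry total bilirubin is 2.0 x ULN with direct below 1.5 x ULN. On study, total bilirubin rises to 2.2 x ULN.

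1. The row omits VAY736 until 1.5 x ULN or less. That is 2.0 - 1.5 = 0.5 x ULN below the entry value, so a return to 2.0 does not permit restart.
2. Section 6.3.1.2 says ibrutinib should also be held when VAY736 is interrupted for toxicity other than an infusion reaction.
3. If 1.5 x ULN is not reached, Section 6.3.1.3 discontinues the patient once the interruption exceeds 28 days. The exception in Section 6.1.5 needs clinical benefit, the investigator's judgment and sponsor agreement.
4. If the value dips to 1.5 x ULN after more than 7 days, VAY736 restarts one level lower. On the provisional levels of Table 6-2 the cut is (3 - 1)/3 = 67%, (1 - 0.3)/1 = 70% or (0.3 - 0.1)/0.3 = 67%. Intermediate levels may be added, which would make the step smaller.
5. A later return to the usual value is again Grade 2, and Section 6.3.1.1 says: "A patient must discontinue treatment if, after treatment is resumed at a lower dose, the toxicity recurs with the same or worse severity".

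**Cycle 1**

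Section 6.3.1 lets a cycle 1 event that meets the DLT criteria resume on return to Grade 1 or the patient's baseline, at a reduced level. Table 6-3 lists Grade 2 total bilirubin lasting more than 7 days as a DLT, so a persistent cycle 1 rise falls under that clause. The price is a lower dose, and discontinuation if the event recurs.

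**Timing outside that clause**

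Suppose the first omitted infusion is C2D1 (day 29), and count the interruption from that day. Day 29 + 28 = day 57 is exactly 28 days, so the limit is first exceeded on day 58.
- Q2W: infusions on days 29, 43 and 57 are missed. Those on days 1 and 15 were given, 2 of the 12 planned in six cycles (17%).
- Q4W: infusions on days 29 and 57 are missed. Day 1 was given, 1 of 6 (17%).

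**Above 3.0 x ULN**

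With an indirect-only elevation and hemolysis excluded, a patient above 3.0 x ULN may continue one level lower without first reaching 1.5 x ULN. A patient between 1.5 and 3.0 x ULN has no such route.

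**The case against.** The strongest answer is that the row does not reach a stable Gilbert's patient. Table 6-4 is titled for adverse drug reactions and its header speaks of worst toxicity. Section 8.1.1 defines an adverse event as something that appears or worsens after consent, and sends conditions already present to Medical History. Section 6.3.1 says delays and adjustments exist so that patients can stay on treatment. This stands for an unchanged entry value.

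It does not settle a rise. A site might attribute a small fluctuation to Gilbert's rather than to the drug, but the row is triggered by the value and does not ask about attribution. Under Section 8.1.2.1, a laboratory abnormality for which the protocol requires a hold is by definition an adverse event, so for such values the argument becomes circular. Even where the row clearly applies, its restart threshold ignores baseline.

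Other objections stand in part:
- Section 6.3.1 does supply a baseline restart, but only for cycle 1 events at DLT level and at a reduced dose.
- The footnote above 3.0 x ULN is not simply more lenient. It requires hemolysis to be excluded and a dose reduction, and leaves continuation to discretion. The lower row allows the full dose if the value resolves within 7 days.
- The contents list shows a Section 6.3.3 whose title and text were removed. The omission can therefore be asserted for the row, not for everything in Section 6.3.
- Amendment 06 reports no escalation patients ongoing and 11 expansion patients on treatment, and SAP Section 1 records early termination endorsed on 22-Sep-2023. Few patients, or none, may still be exposed to the rule.

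**Conclusion.** The conflict is real but narrow. For a Gilbert's patient admitted above 1.5 x ULN, a rise within the band leads to a restart condition below the patient's own baseline, with ibrutinib held as well. The available text offers no baseline relief beyond the cycle 1 clause.

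A reader might infer that every such patient is held from the first on-treatment chemistry, first misses day 15, and is discontinued from day 44 (15 + 28 = 43, exceeded on 44) after 1 of 12 Q2W infusions. The documents do not support that. An unchanged value may lie outside the table, and a persistent cycle 1 rise comes under Section 6.3.1, which accepts baseline. The day-58 illustration is limited to a hold that starts after cycle 1.

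The documents give no frequency of Gilbert's Syndrome, so the number affected cannot be estimated and is probably small. Nothing here shows an effect on the CR rate or on any arm-level rate. The conclusion assumes that the row is applied to on-study values as written and that the removed Section 6.3.3 does not address the point. The change is worth making while anyone is being dosed, and is unnecessary once dosing has ended.

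**What to change.** - In the Table 6-4 row for isolated total bilirubin above 1.5 to 3.0 x ULN, add that patients with Gilbert's Syndrome maintain dose while total bilirubin is below 3.0 x ULN and direct bilirubin is below 1.5 x ULN. Do not also require the value to be no worse than baseline, since that would stop dosing for trivial fluctuation such as 2.0 to 2.1 x ULN.
- Make the restart condition in that row 1.5 x ULN or less, or baseline.
- Put the same Gilbert's/baseline qualifier on the Grade 2 total bilirubin item in Table 6-3. Section 6.3.1 uses those criteria to trigger cycle 1 holds.
- Leave the row for combined AST/ALT and bilirubin elevation unchanged, so that the liver-injury stop is not loosened.

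The cost is the wording of one row and one DLT item, made through an amendment under Section 12.1. Direct and total bilirubin are already in the chemistry panel (Table 7-5), so no new test is needed. If dosing has ended, no change is needed.
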